## 4 Statistical Analysis

### 4.1 Statistical Considerations

This is a cluster-randomized trial with NCORP practice sites being the clusters. Because of the cluster randomized study design, we will apply linear mixed model methodology. The outcome will be the response, and the arm will be the fixed effect. NCORP practice sites will be entered as a random effect independent of residual error. Estimation will be performed using Restricted Maximum Likelihood, and the null hypothesis of zero mean difference between arms will be tested using a F test. The specific NCORP practice site differences will be assessed graphically using Best Linear Unbiased Predictors (BLUP) of the mean response for each NCORP.

All regression analyses will include terms to control for study site and oncologist type. In addition, clinically important socioeconomic variables such as patient gender, age, race/ ethnicity, and cancer variables such as cancer type and treatment status will be used to control for patient-level covariates. In case a key covariate is found to be unbalanced between study arms, it will be included in the model as a potential confounder.

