9. NCORP PRACTICE SITE RANDOMIZATION

A practice site is defined as any practice location within an overarching NCORP designation where oncology physicians and study staff work independently, i.e., do not cross over into another site. Practice sites will be randomized to one of the two study arms by means of a computer-generated randomization table. The randomization process will be determined using R software provided by [name], the lead biostatistician of the URCC NCORP Research Base.

Sites are randomized on a continual basis due to a variety of factors (i.e., a new NCORP Community Affiliate has been added to the URCC NCORP Research Base network, a new oncology practice site has been added to an existing NCORP Community Affiliate, or an oncology practice site that is currently affiliated with an NCORP Community Affiliate has expressed interest in participating in the COACH study). Past accrual to URCC studies (or NCORP Cancer Control studies if URCC accrual information is not available for new Affiliates and sites) is used to stratify each practice site as a **large** accruing (20 or more accruals/year) site or a **small** accruing (less than 20 accruals/year) practice site in order to assure balance in the randomization. The general assumption will be that any new site will be considered "small", unless it is determined based on past accruals that they are large. For new oncology practice sites that meet the definition for being independent (i.e., physicians and staff that do not cross over into another site), the next unassigned randomization allocation, from the randomization table will be used to assign their study arm. The randomization table takes into account size of the practice site. If a new oncology practice site is added at a later time during the study with physicians/staff that also see patients (cross over) at both or multiple practice sites, the new practice site will be assigned to the same study arm as the already randomized practice site where the physician/staff also sees patients.

Once sites have IRB approval on file with the Research Base and at least one member of research staff is trained on all study procedures, they are notified of their randomization allocation by an email from the study PI, [name]. Practice sites names and randomization assignments are saved in the database, this is used to link to which arm each study patient belongs to during patient registration.

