Analysis for Primary Aim 1. This is a cluster randomized trial with NCORP practice sites being the clusters. Because of the cluster randomized study design, we will apply linear mixed model methodology.¹⁰⁴ The total modified HCCQ scores (HCCQ-age) will be the response, and the arm will be the fixed effect. NCORP practice sites will be entered as a random effect independent of residual error. Estimation will be performed using Restricted Maximum Likelihood, and the null hypothesis of zero mean difference between arms will be tested using the F test.¹⁰⁵ The specific practice site differences will be assessed graphically using Best Linear Unbiased Predictors (BLUP) of the mean response for each site.

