#### 3.4.1 Sample Size for NIH-specified Primary Aim

We will utilize the modified HCCQ to address patient satisfaction with communication regarding age-related issues (HCCQ-age). Based on an analysis of the VOICE study, the standard deviation estimate of HCCQ was 2.1. The Intraclass Correlation (ICC) was 0.14 with a 95% confidence interval from 0.01 to 0.51. Because of the large amount of uncertainty in the ICC, we calculated power curves for ICC={0.01, 0.14, 0.51}, with ICC=0.51 being the most conservative. This design (8 sites per arm and 31 subjects per site) has 80% power at the 0.05 significance level to detect a change in HCCQ of 0.6, 1.3 and 2.3 for ICC={0.01, 0.14, 0.51}, respectively. Since the best estimate of the ICC is 0.14, the expected detectable difference is 1.3. This corresponds to an effect size of 0.62. The range of the HCCQ-age scores is 7 (worst possible) to 35 (best possible). Analyses will be based on the HCCQ variables being a continuous variable. We will use a generalized mixed model to confirm robustness. The sample size figure below shows the power for a range of detectable differences (D) for ICC=0.01, 0.14 and 0.51. Small changes in satisfaction scores have been interpreted in other studies to be meaningful given a focus on achievement of high satisfaction scores and the link with reimbursement. In addition to evaluating HCCQ-age using the total score as a continuous variable, we will compare the results for each question as a dichotomous variable (5 vs <5). If the distribution is skewed, we will consider treating HCCQ-age as an ordinal variable in analyses.

Accounting for a small dropout rate of 5% (based on our observational cohort data), the targeted accrual will be **528 patient subjects total**. The dropout rate reflects patients who sign consent but withdraw prior to the audio-recorded baseline visit and capture of HCCQ-age (which will occur within 7 days of baseline visit). To date out of 479 evaluable patients we currently have received 407 baseline HCCQ-ages; 4-6 week HCCQ-ages will be substituted per protocol for 33 patients; there are 19 patients that have no baseline HCCQ-age because they either died or withdrew before the 4-6 week visit, this brings us to a current total of 440 baseline HCCQs to be used in the per protocol analysis.

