### 4.2 Analysis for NIH Primary Aim

The total HCCQ score will be the response, and the analysis will be as described in 4.1. The distribution of the data will be evaluated and if analysis will also include treating HCCQ score as an ordinal variable if warranted.

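### The primary model admits unnamed key covariates when they look unbalanced between arms and omits the site-size stratum; one covariate set should be fixed before unblinding

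*SAP*

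**What the plan says.** SAP 4.1 builds the model in layers, and Protocol 15.1 has the same text.

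- Base: "The outcome will be the response, and the arm will be the fixed effect", with practice site as a random effect.
- Always added: "All regression analyses will include terms to control for study site and oncologist type".
- Also used for adjustment: "clinically important socioeconomic variables such as patient gender, age, race/ ethnicity, and cancer variables such as cancer type and treatment status". The list is introduced by examples, so it is not closed.
- Added conditionally: "In case a key covariate is found to be unbalanced between study arms, it will be included in the model as a potential confounder".

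SAP 4.2 applies all of this to the primary outcome: "The total HCCQ score will be the response, and the analysis will be as described in 4.1". The analysis paragraph for the primary aim in Protocol 15.2 gives only the base layer: "The total modified HCCQ scores (HCCQ-age) will be the response, and the arm will be the fixed effect", again with a random site effect and no covariates.

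Randomisation is stratified by past accrual, large or small. Protocol 9 says: "The randomization table takes into account size of the practice site". SAP 3.3.4 says the same. Neither document names site size as a model term.

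**The concern.** Adjustment is worthwhile when a covariate predicts the outcome. A difference between arms in a covariate says nothing about that. A strong predictor that happens to be balanced would stay out under the conditional rule, and a weak one that happens to differ would go in. The terms key and unbalanced have no definition, metric or threshold. Two statisticians following the documents could therefore fit different primary models to the same data.

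Clustering makes the rule more active. Patient characteristics tend to be alike within a site, so whole-site allocation produces larger chance differences between arms than individual allocation would. A patient-level comparison that ignores site will call them notable too often.

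At stake are a primary HCCQ-age estimate that is settled only after the data are seen, and some precision. Leaving out the stratification factor and repeating the model without covariates in Protocol 15.2 add to the doubt about which model is primary.

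**Working it through.** **1. Models that the text supports**

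- Protocol 15.2, primary aim: arm, random site.
- SAP 4.1 and Protocol 15.1, committed part: arm, random site, oncologist type, and an open list that includes gender, age, race/ethnicity, cancer type and treatment status.
- The same plus any further key covariate judged unbalanced.
- Site size: in none of them.

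**2. The plan's own design figure**

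Inputs from SAP 3.4.1: "This design (8 sites per arm and 31 subjects per site) has 80% power at the 0.05 significance level"; SD 2.1; outcome ICC 0.14 (95% CI 0.01 to 0.51).

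- Design effect = 1 + (31 − 1) × 0.14 = 5.2.
- SE = 2.1 × √(2 × 5.2 / (8 × 31)) = 0.430.
- With a two-sided 5% test and a noncentral t on 14 degrees of freedom, the difference detectable with 80% power is 1.30, as stated. At ICC 0.01 and 0.51 it is 0.65 and 2.29, against 0.6 and 2.3 stated. The 0.6 matches the normal approximation, 0.602.

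This formula has no covariate in it, so the sample size rests on the arm-plus-random-site model.

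**3. How often a trigger might fire by chance**

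The documents give no imbalance test, no covariate ICC and no number of further candidates. All three are assumed here: a patient-level 5% test that ignores site, ICC 0.01 to 0.10, and three independent candidates beyond the named ones.

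- One covariate: p = P(|Z| > 1.96 / √DE), with DE = 1 + (m − 1) × ICC.
- At least one of three: 1 − (1 − p)³.
- 16 sites, m = 31: p = 0.086, 0.215, 0.327 at ICC 0.01, 0.05, 0.10; at least one of three 24%, 52%, 70%.
- 68 sites, m = 496/68 = 7.29: p = 0.057, 0.087, 0.125; at least one of three 16%, 24%, 33%.

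The documents report 68 practice sites as of February 2017, so the second line is closer to the trial. In the sample table in SAP Appendix A, many rows share one randomisation ID and arm. The number of independent units may therefore be below 68, which would move the rates towards the first line.

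**4. Effect on the primary test**

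Simulation, 4,000 trials per scenario, with seven standardised covariates (slope 0.15 SD each) and imbalance called at patient-level p < 0.05; all of these are assumptions. The triggered model starts from arm and site and adds only the flagged covariates. The fixed model always has all seven.

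| Layout and true difference for power | Covariate ICC | Type I, triggered | Type I, fixed | Power, triggered | Power, fixed |
|---|---|---|---|---|---|
| 16 sites of 31; 1.3 | 0 | 4.9% | 4.9% | 79.5% | 80.3% |
| 16 sites of 31; 1.3 | 0.05 | 5.1% | 5.6% | 77.7% | 79.9% |
| 68 sites of 7; 0.75 | 0 | 4.7% | 5.1% | 78.1% | 80.1% |
| 68 sites of 7; 0.75 | 0.05 | 5.3% | 5.5% | 76.8% | 80.3% |

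Monte Carlo standard errors are √(0.05 × 0.95 / 4000) = 0.3 points for type I error and √(0.8 × 0.2 / 4000) = 0.6 points for power. Type I error stays at about 5%. The triggered model loses 1 to 2 points of power with 16 sites and 2 to 3.5 points with 68.

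The simulation lets all seven covariates in by trigger only. The plan always adjusts for its named ones, so its own loss should be smaller.

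If an analyst could pick the most favourable of the unadjusted, triggered and fully adjusted models, type I error would be 5.9% to 7.4% with 16 sites and 6.4% to 7.4% with 68.

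**The case against.** The strongest reply is that most of the adjustment is already committed. The sentences before the conditional one bring in site, oncologist type and the named patient variables whatever their balance. This stands: a reader might infer that the whole covariate set is driven by imbalance, and the text does not support that. The trigger can only add to the committed set.

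A reader might also infer that the rule inflates type I error. The simulation does not show this. The rule looks at covariates, not outcomes, and the 5.9% to 7.4% figures need a free choice among models that neither document plans.

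Nor can one say that a false flag is nearly certain. Rates that high need many independent candidates and the 16-site layout, and the documents specify no such test or list.

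Protocol 15.2 can be read as an incomplete repetition of 15.1 rather than a rival model, since 15.1 covers all regression analyses and SAP 4.2 points to 4.1. That is a fair reading, but the text should say so.

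Imbalance may also be real. Sites learn their allocation before they enrol patients (Protocol 9), and enrolled physicians and site staff then identify candidates (Protocol 5.1), so recruitment could differ by arm. This is a good reason to examine unbalanced covariates in a sensitivity analysis. It does not justify an undefined trigger in the primary model.

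Blinding during analysis (Protocol Appendix X-1) limits steering towards a favoured arm. It does not close the list, because imbalance is visible with masked labels.

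**Conclusion.** The point holds as a gap in pre-specification. An open list and an undefined imbalance rule let the observed data decide the final primary model, and the stratification factor is missing from it. The consequences are analyst latitude and a small loss of precision: about 78–79% against 80% power in the planned layout, and about 77–78% against 80% with 68 sites. These figures depend on the assumed covariate number, slopes, ICC and 5% test, and for the plan as written they are more likely too large than too small. No type I inflation is shown for the rule applied mechanically, and the stated sample size is unaffected. This is a worthwhile improvement, not a threat to the trial's validity.

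**What to change.** Before unblinding, state one primary HCCQ-age model in the same words in SAP 4.1 and 4.2 and Protocol 15.1 and 15.2.

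- Fixed effects: arm, site-size stratum (large/small), oncologist type, age, gender, race/ethnicity, cancer type, and treatment status recorded before the baseline visit. The timing matters because an exploratory aim asks whether the communication influences treatment decisions, so later status could be affected by arm.
- Site as a random effect only. Each site belongs to one arm, so fixed site terms would be confounded with arm.
- Remove the open-ended wording and the imbalance trigger from the primary model. Keep adjustment for other unbalanced covariates as a labelled sensitivity analysis.
- Report the arm-plus-random-site model as supportive; it is the one that the sample size calculation reflects.

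The cost is a wording change and a few degrees of freedom. No new data, patients or procedures are needed.

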### 4.2 Analysis for NIH Primary Aim

The total HCCQ score will be the response, and the analysis will be as described in 4.1. The distribution of the data will be evaluated and if analysis will also include treating HCCQ score as an ordinal variable if warranted.

### 4.3 Analysis for PCORI Primary Aim

The analysis for PCORI Primary Aim will be the same as for NIH Primary Aim, using the number of discussions as the response.

### 4.4 Other Secondary Analyses

#### 4.4.1. Secondary Aim 2

HRQoL will be assessed with the FACT-G and Caregiver HRQoL (burden) will be assessed with the Caregiver Reactions Assessment (CRA). We will include geriatric assessment impairment (at baseline and follow up) to evaluate if these influence patient-reported HRQoL differently in the intervention versus the control group. We will also compare whether the uptake of geriatric assessment recommendations influences patient reported HRQoL and caregiver burden. Data from the intervention arm will be fit to a linear mixed model with the FACT-G or CRA as the outcome, number and percent (number implemented/number recommended) of interventions as the fixed effect, and NCORP site as a random effect independent of residual error. Analyses will be adjusted for treatment status.

#### 4.4.2. Secondary Aim 3

We will compare the effect of the intervention on caregiver satisfaction (the modified health care climate questionnaire-age for the caregiver) using the same linear mixed model methodology.

